Smoking is the number one cause of preventable death in the United States. Given the magnitude of the problem, interventions aimed at promoting smoking cessation have the potential to make large changes in improving health outcomes. Resources to aid with smoking cessation such as telephone-based counseling are generally underutilized. The electronic medical record (EMR) in use at Johns Hopkins has limited decision support to promote referral to the Maryland Quit Line, a free smoking cessation counseling resource. We propose a cluster randomized trial with a waitlist control at 22 Johns Hopkins Community Physicians (JHCP) sites, which offer primary care. The intervention will include a multi-modality intervention to promote provider use of smoking cessation resources which include an Epic-based Best Practice Advisory (BPA) that allows providers to electronically refer to the Maryland State Quit Line, educational materials, and provider visits with Quit Line representatives to review use of smoking cessation practices (academic detailing). Sites will be randomized to one of three arms with increasing support: 1) six-month waitlist control; 2) BPA with optional educational modules; 3) BPA with online educational modules, a quick-reference educational document, and additional academic detailing. We hypothesize that by implementing a new Epic BPA that allows providers to easily refer to the Maryland Quit Line electronically, we will increase use of this resource. We also hypothesize that adding additional educational materials and having Quit Line representatives perform educational outreach visits will further increase use of the Quit Line and will increase prescription of medications to assist with smoking cessation. Ultimately we hope to improve patient care by increasing providers' use the Maryland Quit Line and pharmacotherapy. We hope that the use of these resources will decrease smoking rates and thereby improve patient health and outcomes while improving JHCP quality metrics.

2. Objectives (include all primary and secondary objectives)

The primary goal of this study is to test the effectiveness of instituting an Epic BPA in increasing Maryland Quit Line referrals. The secondary goals are to measure the BPA's effect and the effect of additional provider education on patient engagement with the Quit Line, and on prescription of medications that aid in smoking cessation. A third goal is to obtain initial provider feedback on the BPA to inform roll-out of this BPA across the health system.

Aim 1: In a three-arm, cluster randomized trial, to test the effectiveness of an Epic BPA with provider educational support and provider detailing in provision of smoking cessation services.

Hypothesis 1: An Epic-based BPA to prompt providers to electronically refer people who are ready to quit smoking to the Maryland Quit Line will increase use of this service compared to waitlist control.

Hypothesis 2: An Epic-based BPA supplemented with educational materials and academic detailing will increase Quit-Line referral compared to control.

Hypothesis 3: Additional provider support including educational materials, in-person academic detailing, will increase successful referrals to the Quit Line and prescription of cessation pharmacotherapy compared to waitlist control and BPA only

3. Background

Smoking remains the number one cause of preventable death in the United Sates. Despite decades of declining rates of smoking, the burden of disease caused by smoking remains high. ¹ 22.2% of adults in the U.S. smoke, and 18.4% smoke daily. ² This issue remains a difficult but potentially high-yield area of medicine to improve health outcomes by improving implementation of behavioral and medical therapies. Though phone-based smoking cessation counseling has been shown to be beneficial in improving quit rates³, physicians do not regularly refer their patients for this intervention. There is no decision support tool or automatic referral mechanism embedded in the EMR used at Johns Hopkins. EMR based-interventions have been shown change provider behavior to increase quit line referrals in the outpatient setting ⁴ and the inpatient setting. ⁵ And while prompts embedded in EMRs modestly increase documentation of tobacco use and referral to counseling, more research is needed in this area to improve the effectiveness of these prompts. ⁶ Thus we see an opportunity to institute interventions that is aimed at changing provider behavior and improving patient care.

Educating providers about smoking counseling has been shown to increase their engagement with patients regarding smoking cessation.⁷ One intervention, educational outreach visits, or academic detailing, have been shown to have a small but consistent effect on physician prescribing behaviors.⁸ We hope to use a multi-modality educational intervention, including academic detailing, to enhance the effects of the EMR tools and increase use of smoking cessation resources.

[figure not shown]
By incorporating decision support tools, facilitating use of the Quit Line, and educating clinicians about counseling and pharmacotherapy, we hope to improve the use of these services and increase engagement between clinicians and patients about smoking cessation and to ultimately decrease smoking across the health system

4. Study Procedures

a. Study design, including the sequence and timing of study procedures (distinguish research procedures from those that are part of routine care).

Overview: We propose a cluster randomized trial to test the effectiveness of an Epic-based BPA with and without supplemental education and academic detailing on 1) Quit Line referrals, 2) Patient Quit Line engagement, 3) Prescription of pharmacotherapy, and 4) Smoking cessation. To this end, we will randomize the 35 sites from Johns Hopkins Community Physicians to one of three arms: 1) Cluster C: no intervention initially, BPA added after 6 months; 2) Cluster B: BPA alone with emailed link to MD Quit Line educational material; 3) Cluster A: BPA with online educational modules, a quick-reference educational document, and additional academic detailing. Outcomes will be assessed at 6 and 12 months.

Conceptual Model:

Study design: This will be a **waitlist-control, cluster randomized trial**. JHCP sites will be randomized to Arm A (BPA plus educational interventions), Arm B (BPA only), or Arm C (control group, no intervention). After 6 months, Cluster C will be granted access to the BPA.

Study Population: The study will include all JHCP practices and primary care providers at those sites. JHCP is the largest health specialty group practice in Maryland and cares for over 230,000 patients at 22 practice sites throughout Maryland and Washington, DC. There are approximately 190 adult primary care providers at these sites. Patients will be at least 18 years of age and will be active smokers as indicated in the EMR.

Recruitment: All JHCP sites that provide adult primary care will be included. Providers (physicians and office health professionals like CMAs) will be the target of the intervention. Patients will not directly know about the study but there will be a smoking cessation handout available at each office if patients are interested.

Consent: Because this is an evaluation of an EMR intervention, looking at outcomes in aggregate only, not by provider or by patient, we are applying for a waiver of consent.

Randomization: Randomization to one of the three clusters will occur at the level of each JHCP site. Sites will be stratified by size and a randomization sequence will be generated by an online random number generator.

Intervention: There are several components to the intervention:

- 1. **BPA**: The BPA is an Epic prompt that fires when a provider opens an encounter with a patient who is actively smoking. Providers will be asked to assess smoking cessation readiness and to refer patients to the free Maryland Quit Line if the patient is receptive. The Quit Line will receive an electronic referral with the patient's details. A Quit Line certified smoking cessation counselor will then call the patient at a later date and provide counseling. Receptive patient will receive up to four calls. They will receive counseling from a trained quit coach and be offered free access to NRT.
- 2. **Quit Line**: This free telephone-based counseling service is offered to smoker in Maryland. Services offered include on-the-phone smoking cessation counseling and free nicotine replacement.
- 3. **Consolidated educational hand out**: A one-page hand out will be sent to providers electronically for quick reference. The hand out will include a summarization of counseling, pharmacotherapy, cessation referrals, and coding for cessation counseling.
- 4. **Online modules**: Providers will be directed to optional, self-paced educational modules. The Maryland HABITS program is a series of online modules that include general concepts in smoking cessation, pharmacotherapy, and counseling skills. The modules are text and video based and can be completed in about one hour. Providers can also watch example videos of interviews using these skills.
- 5. **Academic detailing**: Academic detailing is a tool in which educators visit providers in their practice setting, assessing their knowledge base, providing targeted education on a specific topic, and reinforcing the major points of the education. Academic detailing for this trial will include a single session during a clinic day in which counseling experts from the MD Quit Line will visit providers in their practice setting. They will conduct one-on-one question and answer sessions exploring the providers' views on counseling, practices, and knowledge about medications and community resources. The counselors will provide teaching to each provider based on their individual level of knowledge and openness to the education.
 - Detailing as operationalized accommodated individual practice level concerns related to provider time and burden. As such, detailing occurred as an interactive group educational session conducted with a tobacco session experts that was initially offered in-person only and later expanded to include live-webinar with the goal of increasing uptake by providers.

[figure not shown]
Sites will be randomized to three arms:

Arm A: At JHCP sites randomized to Arm A, clinicians will receive an email describing the new smoking BPA, educational materials offered, and a small tutorial on using the BPA and a new smoking cessation smart set in Epic. Education materials will include the educational hand out and academic detailing from Maryland Quit Line counselors.

Arm B: At JHCP sites randomized to Arm B, clinicians will receive an email describing the BPA and order set, along with internet links to MD Quit Line without additional supplemental education. This will allow us to compare use of the BPA alone to the BPA plus supplemental education.

Arm C: This last Arm will serve as the waitlist control, receiving no intervention initially. After six months, clinicians in Arm C will receive either the BPA intervention similar to Arm B without additional education or BPA + education, similar to ARM A Arm C not only serves as a control condition, but also allows for the gradual roll out of the BPA across JHCP to ensure that the MD state Quit Line can handle the increase in referral volume.

These three arms will help us determine how best to roll out this BPA across the Hopkins Health System.

1 Year Analysis: Primary and Secondary outcomes measured

Control: JHCP sites randomized to Arm C will receive no intervention, serving as controls for the first 6 months of the trial period. After six months, Arm C will be randomized to receive either the Epic BPA or the BPA + education..

Measures:

	Outcome	How outcome is measured	
Primary outcome	Provider electronic referrals to the Maryland Quit line	Orders are tracked though Epic	
Secondary outcomes	Patient prescribed nicotine replacement, bupropion, or varenicline	Orders are tracked though Epic	
	Patient engagement with Quit Line (number of interactions, use of services)	Maryland Quit Line collects data during encounters and will provide this information to the study group	
	Patient-reported smoking cessation after 1 year	The patient's smoking status as logged in Epic	

Provider feedback on BPA:

We will obtain initial provider feedback on the BPA 6 months after initial roll out. Only providers at sites where the BPA has been implemented will be asked to fill out the survey. We will not collect names, but will collect site (to verify that BPA was active), years in practice and provider type. On the survey we will include the statement that participating in this survey serves as consent to the study. To protect confidentiality, no names or DOB will be collected. Data will be stored on the Johns Hopkins Secure Server and site data will be presented only in aggregate, by cluster (e.g. we will not report on individual sites, but rather by assigned cluster condition).

- b. Study duration and number of study visits required of research participants. Study duration will be 1 year.
- c. Blinding, including justification for blinding or not blinding the trial, if applicable.

Providers will be notified about this implementation study and will know what arm they have been randomized to.

- d. Justification of why participants will not receive routine care or will have current therapy stopped. The control group will receive routine care from their provider, which can include counseling, pharmacotherapy, and Quit Line referral. The study will not prevent any provider from assisting smokers to quit with all guideline-based care.
- e. Justification for inclusion of a placebo or non-treatment group.

While implementing the BPA to increase electronic referrals to the Quit Line is quite easy since the interface is already built, it is important for the health system to determine the added value of additional training for providers to use this referral effectively. We think a delay of 6 months in the added training does not increase risk beyond expected benefits. In addition, the Maryland State Quit Line will need this time to see if they can handle the increased volume.

To evaluate the effectiveness for the BPA, we feel a control group is needed. Arm B (the educational control) is necessary to evaluate whether the BPA with education is better than a BPA launched alone without education.

- f. Definition of treatment failure or participant removal criteria. Not applicable.
- g. Description of what happens to participants receiving therapy when study ends or if a participant's participation in the study ends prematurely.

 Not applicable.

5. Inclusion/Exclusion Criteria

BPAInclusion criteria: Sites are JHCP primary care practices.

Exclusion criteria: There are no exclusion criteria.

Survey: Providers will be included if they practice at the original sites randomized to either the BPA or the BPA + education

6. Drugs/ Substances/ Devices

- a. The rationale for choosing the drug and dose or for choosing the device to be used. Not applicable.
- b. Justification and safety information if FDA approved drugs will be administered for non-FDA approved indications or if doses or routes of administration or participant populations are changed.

Not applicable.

c. Justification and safety information if non-FDA approved drugs without an IND will be administered.

Not applicable.

Date: _____November 3, 2017

Principal Investigator: [name] MPH

Application Number: **IRB00124880**

7. Study Statistics

a. Primary outcome variable.

• Provider electronic referrals to the Maryland Quit line

- b. Secondary outcome variables.
 - Patient prescribed nicotine replacement, bupropion, or varenicline
 - Patient engagement with Quit Line (number of interactions, use of services)
 - Patient-reported smoking cessation after 1 year
- c. Statistical plan including sample size justification and interim data analysis.

Based on prior research with a comparable tool used in the inpatient setting where compared to control arm physicians, intervention physicians were more likely to order tobacco treatment medication (24% v. 9%, P = 0.0001, Fisher's exact test), and make a referral to the state smokers' quitline (19% v. 0%, P < 0.0001, we expect a 20% absolute increase in the percentage of the population of active smokers who are referred to the Quit Line among providers that receive the BPA, and a 30% increase among providers receiving the BPA + educational materials/detailing, compared to the control condition. Our main outcome, is quitline referral, which is a dichotomous outcome. We will use logistic regression accounting for clustering by site and provider to determine the difference in quit-line referral between the BPA only arm, and the waitlist control (B vs C), the BPA + education and the waitlist control (A vs C), and the BPA + educational materials arm and the BPA only arm (A vs B). The two primary testing contrasts will be B vs C and A vs C, each will be evaluated at type I error of 0.025 to safeguard the overall type I error for testing the 2 primary contrasts. The secondary contrast of A vs B is exploratory in nature, to estimate the potential incremental increase in quitline referral with additional provider education. The difference in % referral between arms and its corresponding 95% CI will be calculated. Due to the design of cluster randomization by sites, provider level and patient level characteristics that are not balanced by randomization between arms will be adjusted for in the logistic regression model.

In this 3-arm trial, we expect 7 JHCP sites per arm, with an average cluster size of 1000 smokers per site (based on current patient numbers in the clinics, number of smokers, and proportion willing to quit). Assuming intracluster correlation of 0.1, and a 5% quitline referral in the control Arm C, we will have 88.6% power to detect a 20% absolute increase in quitline referral in Arm B when testing the contrast of B vs C using a Z-test at type I error of 0.025, and 99.4% power to detect a 30% absolute increase in quitline referral in Arm A when testing the contrast of A vs C using a Z-test at type I error of 0.025.

For the survey, qualitative answers will be read by Drs. [name] and [name], and coded for recurrent themes. These themes will then be summarized for study investigator to inform future roll out of the BPA. Quantitative data will be summarized using descriptive statistics. There are approximately 190 providers at JHCP. We anticipate that 2/3 of providers will have interacted with the BPA, as part of the initial BPA roll out. Thus our maximum sample size is 125 providers.

d. Early stopping rules.
None

8. Risks

a. Medical risks, listing all procedures, their major and minor risks and expected frequency.

We do not expect any more risk to patients than those occurring during the routine management of smoking cessation. We are not proposing any changes to treatment that are not based on evidence-based guidelines. The main risk is some providers and patients will not be exposed to implementation packaged for 6 months.

b. Steps taken to minimize the risks.

Providers have been able to refer smokers to the MD Quit Line for several years and this will still be possible. The delay in full implementation support will only be for 6 months.

- c. Plan for reporting unanticipated problems or study deviations.

 The principal investigator will report any study deviations to Johns Hopkins Institutional Review Board (IRB).
- d. Legal risks such as the risks that would be associated with breach of confidentiality. None expected.
- e. Financial risks to the participants.
 Financial risk to participants will be minimal but may include the cost of medications they would have otherwise not been prescribed.
- f. Risks Related to Survey Administration: To protect confidentiality, no names or DOB will be collected. Data will be stored on the Johns Hopkins Secure Server and site data will be presented only in aggregate, by cluster (e.g. we will not report on individual sites, but rather by assigned cluster condition).

9. Benefits

a. Description of the probable benefits for the participant and for society.

Patients: All patients will have improved access to smoking cessation support through the state Quit Line. Some patients will have this support immediately and some after 6 months.

Providers: Providers will benefit from access to materials to improve the medical knowledge. They will have access to tools that will make prescribe more efficient, potentially improving work flow. If patients quit as a results of these interventions, the provider's quality metrics will improve.

Society: As discussed previously, smoking remains the number one cause of preventable death in the United States. If our intervention is shown to improve use of state Quit Line, and especially if it shows an improvement in successful smoking cessation, it may serve as a model for implementation more broadly. Such a finding may also be used for continued funding of the BPA and electronic referral system.

10. Payment and Remuneration

a. Detail compensation for participants including possible total compensation, proposed bonus, and any proposed reductions or penalties for not completing the protocol.

We do not plan to provide compensation to medical providers or patients.

11. Costs

a. Detail costs of study procedure(s) or drug (s) or substance(s) to participants and identify who will pay for them.

There are no direct costs associated with this trial.

Education material will be prepared and provided by the study team at no cost. Maryland Quit Line services are offered for free to patients.				

References

- 1. Department of Health U, Services H, for Disease Control C, Center for Chronic Disease Prevention N, Promotion H, on Smoking O. Executive Summary (The Health Consequences of Smoking—50 Years of Progress: A Report of the Surgeon General).

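### The prescribing comparison does not use each site's earlier prescribing rate, which costs precision and leaves it open to chance imbalance with about seven sites per arm

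*Combined protocol and SAP*

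**What the plan says.** - **Timing.** The Overview in section 4a states: "Outcomes will be assessed at 6 and 12 months". No window before go-live, baseline rate or baseline-adjusted model is described in sections 4 to 7.
- **Outcome and source.** Sections 4a (Measures) and 7b list "Patient prescribed nicotine replacement, bupropion, or varenicline" as a secondary outcome. For its source, Measures states: "Orders are tracked though Epic". Hypothesis 3 in section 2 expects added provider support to raise prescribing over both the waitlist control and BPA only.
- **Prescribing without the intervention.** Section 4d states: "The control group will receive routine care from their provider, which can include counseling, pharmacotherapy, and Quit Line referral".
- **Handling of site differences.** Randomisation is by site, stratified by size (section 4a). Section 7c accounts for clustering by site and provider, and adds that "provider level and patient level characteristics that are not balanced by randomization between arms will be adjusted for" in the logistic model. That model is written for referral. Section 7c gives no analysis or power for prescribing.
- **Planning figures.** For referral, section 7c states "we expect 7 JHCP sites per arm, with an average cluster size of 1000 smokers per site" and "Assuming intracluster correlation of 0.1, and a 5% quitline referral in the control Arm C". On the two primary contrasts it states: "each will be evaluated at type I error of 0.025".

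**The concern.** An ICC of 0.1 implies wide differences between sites: a between-site SD of about 9 points around a 9% rate and 13.5 points around 24%. With seven sites per arm, the average of those differences will vary by chance from one randomisation to the next, and this variation dominates the standard error. A site's own earlier rate is likely to be the best single predictor of its later rate, and neither the stratification nor the adjustment rule uses it.

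At stake is the prescribing part of Hypothesis 3. The Background describes the effect of academic detailing on prescribing as small though consistent, and an imprecise comparison could easily miss such an effect. Recruiting more sites is not an open route, because all JHCP adult primary care sites are already included.

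**Working it through.** **Inputs from section 7c:** k = 7 sites per arm, m = 1000 smokers per site, ICC = 0.1; prescribing 24% v. 9% from the cited inpatient study, the only prescribing rates given. (Section 1 and the Study Population text give 22 sites and the Overview gives 35; seven per arm fits 22.)

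**Assumptions:** the referral ICC applies to prescribing; 24% v. 9% applies here; the correlation r between a site's underlying rates before and after go-live is 0.3 to 0.8. The documents do not give r.

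**Step 1. Reproduce the plan's power for referral.** Design effect = 1 + 999 × 0.1 = 100.9, so effective n = 7000/100.9 = 69.4 per arm. With an unpooled Z-test at two-sided 0.025 (z = 2.241):
- 5% v. 25%: SE = √[(0.0475 + 0.1875)/69.4] = 0.0582; power = Φ(0.20/0.0582 − 2.241) = 88.4% (stated 88.6%).
- 5% v. 35%: SE = √[(0.0475 + 0.2275)/69.4] = 0.0630; power = Φ(0.30/0.0630 − 2.241) = 99.4% (stated 99.4%).

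The plan's inputs are therefore being read as intended.

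**Step 2. Prescribing without a baseline.** The sum of p(1−p) over the two arms is 0.09 × 0.91 + 0.24 × 0.76 = 0.0819 + 0.1824 = 0.2643.

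SE² = 0.2643 × [ICC + (1−ICC)/m]/k = 0.2643 × 0.1009/7 = 0.00381, so SE = 6.2 points and the 95% half-width is 12.1 points. Z power at two-sided 0.05 = Φ(0.15/0.0617 − 1.96) = 68%. A t-test on 12 df gives 61%.

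**Step 3. With the site's pre-period rate as covariate.** The between-site part is multiplied by (1 − r²):

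SE² = 0.2643 × [ICC(1 − r²) + (1−ICC)/m]/k. At r = 0.7: 0.2643 × (0.051 + 0.0009)/7 = 0.00196, so SE = 4.4 points.

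| r (assumed) | SE, points | Power, Z | Power, t |
|---|---|---|---|
| no baseline | 6.2 | 68% | 61% (12 df) |
| 0.3 | 5.9 | 72% | 64% (11 df) |
| 0.5 | 5.4 | 80% | 72% (11 df) |
| 0.7 | 4.4 | 92% | 87% (11 df) |
| 0.8 | 3.7 | 98% | 95% (11 df) |

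Allowing for sampling error in a pre-period rate based on 1000 smokers changes r = 0.7 only to 0.694, so the table barely moves. At r = 0.7 the variance roughly halves, as if each arm had 13 to 14 sites.

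**Step 4. Chance imbalance.** If every arm prescribed at 9% with no effect, SE = √(2 × 0.0819 × 0.1009/7) = 4.9 points. Two arms would then differ by more than 5 points in about 30% of randomisations. With adjustment at r = 0.7 the SE is 3.5 points and the figure about 15%.

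**Step 5. A smaller ICC.** At ICC 0.05, SE² = 0.2643 × 0.05095/7, so SE = 4.4 points, half-width 8.6 points and Z power 93% without a baseline. At r = 0.7 the half-width falls to 6.2 points. At ICC 0.02 or below, Z power exceeds 99% without a baseline.

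**The case against.** A randomised comparison of outcomes after go-live is a valid design. Chance differences between sites enter the standard error through the ICC, and false positives are held at the test level. A reader might infer that the plan cannot tell an effect of education from long-standing habits at a site, or that the result will be biased. The documents do not support this, because sites are randomised. Nor does the comparison absorb every prior difference: size stratification removes part, and so would the covariate rule if it were extended to prescribing.

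The power figures are also conditional. The ICC of 0.1 is a planning value for referral, and at 0.05 most of the power deficit disappears. The 24% v. 9% compares a prompt with control among inpatient physicians, so it says little about A v. B, the contrast that isolates education. The calculation is linear on site proportions, while the plan's model is logistic, so the gain there may differ somewhat. At r = 0.3 the gain is small. That usable earlier orders exist at every site is a strong inference, not a statement in the plan, and a baseline shown only in a missing figure cannot be excluded.

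All of this stands. It limits the size and certainty of the gain but does not remove it: in the calculation, power rises at every r from 0.3 to 0.8, even after the lost degree of freedom.

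**Conclusion.** The point holds as one of efficiency for a secondary outcome. The readable plan leaves out a predictor that is probably available and cheap, in a comparison with few sites. At the plan's ICC, and with 24% v. 9% carried over, adjustment raises power at two-sided 0.05 from 68% to between 72% and 98% (Z), or from 61% to between 64% and 95% (t), for r from 0.3 to 0.8. At ICC 0.05 the benefit is mainly a narrower interval.

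A reader might extend the point to the primary outcome, but that goes too far. The Background says that the EMR had no automatic referral mechanism. Although routine care could include referral, electronic referrals before go-live may be few or unrecorded, and adjustment may add little. It would also go too far to conclude that the prescribing comparison is underpowered: the plan sets no power target or alpha for it, and its ICC is unknown.

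**What to change.** In section 4a, state that the Epic extract will also cover cessation-medication orders among active smokers at each site for the six months before go-live. In section 7c, specify the prescribing model, which the plan now lacks, and enter the site's pre-period rate as a prespecified covariate in all contrasts, whether or not the arms look unbalanced.

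Use the rate as a covariate, not a change score. With equal variances before and after, a change score multiplies the between-site variance by 2(1 − r), which is 1.4 at r = 0.3 and exceeds 1 whenever r is below 0.5. The covariate multiplies it by 1 − r², which is 0.91 at r = 0.3.

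Do the same for referral only if referrals before go-live are recorded.

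The cost is a longer Epic query, possibly a wider scope for the consent waiver, and one site-level degree of freedom (12 to 11). There is no added burden on sites, providers or patients.

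### Cessation is defined only at 1 year, when every Arm C site has been exposed for about six months, so its contrasts with Arm C have no unexposed control

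*Combined protocol and SAP*

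**What the plan says.** - **Definition.** Section 7b and the Measures table in section 4a both give the endpoint as "Patient-reported smoking cessation after 1 year". The table gives its source as "The patient's smoking status as logged in Epic". No other outcome in either list has a time point in its definition.
- **Control period.** Section 4a (Control) describes Arm C sites as "serving as controls for the first 6 months of the trial period".
- **Switch.** Section 4a (Study design) says: "After 6 months, Cluster C will be granted access to the BPA". Section 4a (Control) says: "After six months, Arm C will be randomized to receive either the Epic BPA or the BPA + education". The Arm C description also allows either package.
- **Length.** Section 4b: "Study duration will be 1 year".
- **Overview.** The opening paragraph of section 4a ends its list of what the trial tests with "3) Prescription of pharmacotherapy, and 4) Smoking cessation", and the same paragraph says: "Outcomes will be assessed at 6 and 12 months".
- **Analysis.** Section 7c describes a model and contrasts for referral only. It gives no analysis time point, no method for cessation, and no rule for handling the Arm C switch.

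**The concern.** A waitlist control supports a comparison with no intervention only while the waitlist lasts. Cessation is read, by its definition, about six months after the waitlist has ended. B vs C and A vs C at that point compare sites that started early with sites that started late.

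This is separate from the time window of the referral analysis. Referral orders build up over the study and can be counted to month 6. Cessation is a status tied by definition to 1 year, so fixing the referral window would leave it as it is.

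Cessation is one of the four outcomes named in the Overview, and section 9 (benefits to society) gives it particular weight alongside Quit Line use. Section 4e itself argues that a control group is needed to evaluate the BPA. If a 12-versus-6-month comparison were read as BPA versus no BPA, a real effect on quitting could look small or absent.

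**Working it through.** **1. The plan's own figures.** The documents state no rate, effect size or power for cessation. The only power figures are for referral, and they reproduce closely. The design effect is 1 + 999 × 0.1 = 100.9, so the effective sample is 7000 / 100.9 = 69.4 per arm. An unpooled Z-test at two-sided 0.025 gives 88.4% for 5% vs 25% (stated 88.6%) and 99.4% for 5% vs 35% (stated 99.4%). These figures have no bearing on cessation.

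**2. Exposure at each reading, from section 4a.**

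| Reading | Arm A | Arm B | Arm C |
|---|---|---|---|
| Month 6 | 6 months | 6 months | 0 |
| Month 12 | 12 months | 12 months | about 6 months |

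The reading in the endpoint definition is month 12. A and B do not switch, so A vs B is unaffected.

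**3. Share of the 12-month effect still visible against Arm C.** Let E(t) be the effect after t months of exposure. If Arm C receives the same package, the share kept is [E(12) − E(6)] / E(12). All the curves below are assumptions.

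| Assumed curve | Share kept | Share lost |
|---|---|---|
| Linear: (12 − 6)/12 | 50% | 50% |
| Early-saturating, 1 − exp(−t/τ), τ = 24, 12, 6, 3 months | 44%, 38%, 27%, 12% | 56%, 62%, 73%, 88% |
| Linear after a lag of 1, 2, 3, 4, 6 months | 55%, 60%, 67%, 75%, 100% | 45%, 40%, 33%, 25%, 0% |

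**4. Mixed packages in Arm C.** Assume linear effects, an A:B effect ratio of 1.5 (borrowed from the plan's 30:20 on referral) and half of the Arm C sites on each package. In units of B's 12-month effect, Arm C gains 0.5 × (0.5 × 1 + 0.5 × 1.5) = 0.625. B vs C keeps 1 − 0.625 = 37.5%. A vs C keeps (1.5 − 0.625)/1.5 = 58%.

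**5. Illustration in percentage points.** Assume even accrual at 5% per year without the BPA, 8% with the BPA and 10% with BPA plus education. The full 12-month effects are then 3 points (B) and 5 points (A). Arm C at 12 months shows 2.5 + 4.0 = 6.5% if all its sites get the BPA, 2.5 + 5.0 = 7.5% if all get BPA plus education, and 7.0% if split evenly.

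| | B vs C | A vs C |
|---|---|---|
| Month 12, C all BPA | 8.0 − 6.5 = 1.5 | 10.0 − 6.5 = 3.5 |
| Month 12, C split | 8.0 − 7.0 = 1.0 | 10.0 − 7.0 = 3.0 |
| Month 12, C all BPA plus education | 8.0 − 7.5 = 0.5 | 10.0 − 7.5 = 2.5 |
| Month 6, C unexposed | 4.0 − 2.5 = 1.5 | 5.0 − 2.5 = 2.5 |

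B vs C keeps 17% to 50% of its effect and A vs C keeps 50% to 70%. The month-6 contrast equals the largest 12-month figure for B and the smallest for A.

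**The case against.** **The Overview may already provide a month-6 reading.** It lists cessation and puts outcome assessment at 6 and 12 months. A reader might infer from the endpoint definition that no smoking status is read while Arm C is unexposed. The documents do not support going that far: a month-6 reading is implied. Section 4a also has a line on a one-year analysis that looks like a label from a figure not reproduced in the text, so the lack of a six-month counterpart proves nothing. What remains is a conflict: the general sentence gives two time points, the two specific definitions give one, and section 7c does not settle it.

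**The size is not in the documents.** A reader might infer that the endpoint understates any effect by half or more. That does not hold. The rates in step 5 are invented for illustration, and even there A vs C loses only 30% to 50%. A vs B loses nothing, and with a six-month lag neither does a contrast with C. The objection stands in full against any single figure.

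**Reversal of B vs C.** A reader might infer that B could fall below C, because some switched sites may hold a stronger package. The parts of section 4a differ on whether any Arm C site gets education. With linear effects and A:B ratio r, an even split needs 0.25 + 0.25r > 1, so r > 3. If every Arm C site got education, 0.5r > 1 is needed, so r > 2. Nothing in the plan suggests such a ratio.

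**Consequences.** Section 9 puts Quit Line use first and cessation in addition, so wider implementation does not rest on cessation alone. No cessation test is specified, so a misread null result is a risk rather than a planned conclusion.

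**The fix does not promise a larger contrast.** This also stands. With a linear effect and the same package, E(6) equals E(12) − E(6). What is gained is an unexposed comparator.

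**Conclusion.** The point holds in a limited form. As defined in section 7b and the Measures table, cessation has no unexposed comparison with Arm C. B vs C and A vs C at 1 year compare early with delayed roll-out and are probably attenuated. The loss is about half if the effect is linear in exposure and Arm C gets the same package, and ran from 0% to about 88% over the other curves tried. The documents give no basis for choosing among these, so confidence in any one magnitude is low. The definition also conflicts with the two assessment times in the Overview. This is a secondary endpoint, and the primary referral claim is not affected.

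**What to change.** - Reconcile the Overview and Measures table in section 4a with section 7b. Add to the table and to 7b a month-6 Epic smoking status for all baseline smokers, taken before any Arm C site goes live, and name it as the cessation comparison against Arm C.
- Keep the 12-month status for A vs B.
- Report A or B vs C at 12 months as early versus delayed roll-out, not as an effect against no intervention.
- Make the parts of section 4a agree on what Arm C receives after month 6, since the 12-month contrasts depend on it.

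The cost is one more extraction of a field already held in Epic, plus wording changes. The downside is that the controlled comparison covers only six months. It does not show one-year abstinence, it may miss quitting that is slow to appear, and it should not be counted on to give a larger contrast. That is a reason to report both time points.
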